## 10. SAFETY AND TOLERABILITY

Safety analyses will be conducted using the Safety Analysis Set at both the primary and final analysis. At the primary analysis, all available data will be summarized. Unless otherwise noted, all safety analyses will be conducted using on-study data. All safety analyses specified below refer to the double-blind period only, except where noted. If >5% of patients initiate RRT while on study, select summaries excluding results after initiation of RRT may be prepared.

### 10.1. Adverse Events

AE data will be collected from the time that signed informed consent is obtained until the patient fully completes his/her participation in the study.

All AE summaries will be restricted to TEAEs, which are defined as any AE that newly appears, increases in frequency, or worsens in severity following the initiation of study medication. If it cannot be determined whether the AE is treatment-emergent due to a partial onset date, then it will be counted as treatment-emergent. Verbatim terms will be coded to PTs and SOC using MedDRA.

Each AE summary will be displayed by treatment group. Summaries that are displayed by SOC and PT will be ordered by descending order of incidence of SOC and PT within each SOC. Summaries of the following types will be presented:

- Overall summary of TEAEs
- Patient incidence of TEAEs and the total number of entries by SOC and PT
- Patient incidence of TEAEs and the total number of entries by PT in descending order
- Patient incidence of TEAEs by SOC, PT, and highest severity. At each level of patient summarization, a patient is classified according to the highest severity if the patient reported 1 or more events. AEs with missing severity will be considered severe for this summary.
- Patient incidence and total number of entries of severe TEAEs by SOC and PT. AEs with missing severity will be considered severe for this summary.
- Patient incidence of TEAEs by SOC, PT, and closest relationship to study medication (Related/Not Related). Related AEs are those with relationships reported as “Possibly Related” or “Related” and unrelated AEs are those with relationships reported as “Unlikely Related” or “Not Related.” At each level of patient summarization, a patient is classified according to the closest relationship to study medication if the patient reported 1 or more events. AEs with a missing relationship will be considered related for this summary.
- Patient incidence and total number of entries of related TEAEs by MedDRA SOC and PT. AEs with a missing relationship will be considered related for this summary.
- Patient incidence of serious TEAEs and the total number of entries by SOC and PT
- Patient incidence of TEAEs leading to treatment discontinuation by SOC and PT

- Patient incidence and total number entries of treatment-emergent adverse events of interest (AEOIs) by SOC and PT
- Patient incidence and total number of entries of TEAEs associated with safety topics of interest by PT
- Patient incidence and total number of entries of related TEAEs associated with safety topics of interest by PT
- Patient incidence and total number of entries of serious TEAEs associated with safety topics of interest by PT

### 10.1.1. Adverse Events of Interest (AEOIs)

Abnormal liver function tests that meet the below criteria are considered AEOIs:

- The abnormality represents a new elevation in alanine aminotransferase (ALT) or aspartate aminotransferase (AST)  $>3 \times \text{ULN}$ , with or without an elevation of total serum bilirubin  $>2 \times \text{ULN}$
- The abnormality represents a 2-fold increase in ALT or AST above the baseline value in patients who had elevated values prior to starting study medication.

As described in [Section 10.1](#), patient incidence of treatment-emergent AEOIs will be summarized by treatment group.

In order to explore the relationship between liver function abnormalities and study medication, the following time-to-event analysis will be performed:

- Time to first onset of treatment-emergent AEOI
  - The time to the start of the first occurrence will be calculated by the date of onset of first AEOI – date of first dose of study medication + 1.
  - Patients who never reported an AEOI will be censored at the date of completion or discontinuation in randomized treatment period or data cut-off date of analysis, whichever is earlier .
- Time to resolution of the most severe treatment-emergent AEOI
  - If multiple treatment-emergent AEOIs with the same PT with increasing severity were reported for the same patient, the time to resolution will be calculated by the date of resolution of the most severe event – start of the initial event + 1.
  - Otherwise, the time to resolution will be calculated by the date of resolution of the event – start of the event + 1.
  - Patients whose most severe treatment-emergent AEOI is ongoing will be censored at the date of completion or discontinuation in randomized treatment period or data cut-off date of analysis, whichever is earlier.
  - Only patients who had reported a treatment-emergent AEOI are included in this analysis.

The analysis of time to event will include the number of patients with an event, the number of patients without an event (censored), descriptive statistics of time for those with an event, and range in days for all patients. KM estimates will be calculated by treatment group. The quartiles, including the median time-to-event and their respective 2-sided 95% CIs, will be presented. KM estimates will be plotted as a cumulative probability plot for each treatment group with the number at risk identified.

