### **10.3. Adverse Events of Interest**

#### **10.3.1. Abnormal Liver Function Test Results**

Abnormal liver function test results that meet at least one of the following criteria below will be considered AEOIs and must be reported to the Sponsor's Medical Monitor within 24 hours of awareness:

- The abnormality represents a new elevation in ALT or AST >3 times the upper limit of normal (ULN), with or without an elevation of total serum bilirubin >2 times ULN.
- The abnormality represents a 2-fold increase in ALT or AST above the baseline value for the double-blind period (ie, Day 1) in patients who had elevated values prior to starting study medication or a 2-fold increase in ALT or AST above the baseline value for the open-label extension period (ie, Week 114) in patients who had elevated values prior to starting open-label sparsentan.

In such instances, the following steps should be taken:

1. Temporarily discontinue study medication.
2. Perform repeat testing of ALT, AST, liver-specific alkaline phosphatase (ALP), and total bilirubin within 48 to 72 hours to confirm the abnormalities.
3. If the abnormality is confirmed by repeat results, the following should be done:
  - a. Complete an AEOI Report Form that documents both the liver function test findings and any associated signs or symptoms, and report by email to the SAE contact on the [Study Contact Information](#) page of this protocol.
  - b. Monitor liver enzymes and serum bilirubin 2 or 3 times weekly. The frequency of re-testing can decrease to once weekly or less if the abnormalities stabilize and the patient is asymptomatic.
  - c. Perform additional testing to evaluate liver function, as appropriate (eg, international normalized ratio [INR] and direct bilirubin).

4. Do not resume study medication until monitoring indicates abnormalities have resolved or stabilized.

Patients are not allowed to resume study medication if they have the following:

- ALT or AST >8 times ULN.
- ALT or AST >5 times ULN for more than 2 weeks.
- ALT or AST >3 times ULN and total bilirubin >2 times ULN or INR of >1.5.
- ALT or AST >3 times ULN, with symptoms of fatigue, nausea, vomiting, right upper quadrant pain or tenderness, fever, rash, and/or eosinophilia (>5% eosinophils).

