Management of such patients should be closely coordinated with the Sponsor's Medical Monitor. In addition to monitoring liver function tests, the Investigator should perform other relevant clinical and laboratory measurements to identify potential causes of the abnormalities (eg, acute viral hepatitis types A, B, C, D, and E; autoimmune or alcoholic hepatitis; non-alcoholic steatohepatitis; biliary tract disease or exposure to hepatotoxic medications or environmental chemical agents). Additionally, patients who demonstrate elevated liver enzymes a second time after re-introduction of the study medication may continue in the clinical study; however, they will not receive study medication for the remainder of the trial.

Cases of increased liver function tests will always be considered serious (ie, medically important) if they meet both the following criteria:

- Study medication is suspected to have caused hepatocellular injury, generally shown by a confirmed elevation of 3-fold or greater above ULN in ALT or AST.
- The ALT or AST elevations are accompanied by a total bilirubin >2 times the ULN or INR of >1.5 without initial findings of cholestasis (elevated serum liver-specific ALP).

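### SAP 10.1.1 starts the time to resolution of the most severe liver AEOI at the initial same-term event even if that event had already resolved, so a worse recurrence is credited with the event-free gap

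*SAP*

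**What the plan says.** SAP 10.1.1 defines liver test abnormalities as the AEOIs and plans two time-to-event summaries by treatment group. The second is the time to resolution of a patient's most severe treatment-emergent AEOI. Only patients with an AEOI enter it.

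- **Series of worsening events.** "If multiple treatment-emergent AEOIs with the same PT with increasing severity were reported for the same patient, the time to resolution will be calculated". The end of the interval is fixed "by the date of resolution of the most severe event", and the origin subtracted from it is given as "start of the initial event + 1".
- **All other cases.** "Otherwise, the time to resolution will be calculated by the date of resolution of the event" less that event's own start, plus 1.
- **Unresolved cases.** "Patients whose most severe treatment-emergent AEOI is ongoing will be censored at the date of completion or discontinuation in randomized treatment period" or at the data cut-off, whichever comes first.
- **Outputs.** Kaplan-Meier quartiles with confidence intervals, a cumulative probability plot, a range in days and "descriptive statistics of time for those with an event".

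Protocol 10.3.1 has study medication interrupted when such an abnormality appears. On restarting it says: "Do not resume study medication until monitoring indicates abnormalities have resolved or stabilized". It then deals with a second episode: "patients who demonstrate elevated liver enzymes a second time after re-introduction of the study medication may continue in the clinical study", but without further study medication.

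**The concern.** The rule for worsening events suits one episode entered as several records while it gets worse. In that case the first record's start is the right origin. The text does not limit the rule to that case, however. It does not ask whether the initial event had ended, and it does not subtract time without an abnormality.

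The protocol's restart pathway can produce two separate, fully dated episodes in one patient. If the second is worse and carries the same preferred term, the SAP's formula joins them. The result is no longer how long the most severe event took to resolve, which is what the analysis is labelled to show. Two reversible episodes then appear as one prolonged one, and the fact that the abnormality came back after re-introduction does not show in this output. Few patients may contribute to it, so individual inflated times can matter to the upper quartile and the range.

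**Working it through.** The plan gives no figure to reproduce: it states no expected number, duration or recurrence rate for AEOIs. The check applies the SAP's own formulas to assumed dates.

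**Step 1: one patient, two episodes (assumed dates).** The first AEOI runs from Day 60 to Day 80 and resolves. A second with the same preferred term runs from Day 200 to Day 228.

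- Second event more severe: 228 − 60 + 1 = **169 days**.
- Second event equally severe, so the other rule applies: 228 − 200 + 1 = **29 days**.

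The 169 days break down as follows:

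- first episode: 80 − 60 + 1 = 21
- event-free gap, Days 81-199: 199 − 81 + 1 = 119
- second episode: 29
- total: 21 + 119 + 29 = 169

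The difference of 169 − 29 = 140 days comes entirely from the severity comparison. The speed of resolution is identical.

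**Step 2: dependence on the gap.** Take two assumed 28-day episodes, the first on Days 85-112, the second worse and under the same term, separated by g resolved days. The SAP formula gives 28 + g + 28 = 56 + g.

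| Gap g (days) | SAP rule (days) | Most severe event from its own start (days) |
|---|---|---|
| 0 | 56 | 28 |
| 28 | 84 | 28 |
| 84 | 140 | 28 |
| 168 | 224 | 28 |
| 336 | 392 | 28 |
| 560 | 616 | 28 |

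At g = 0, with continuing records of one worsening episode, 56 days is the sensible answer. At every larger gap the excess over 28 days is the first episode plus the gap, although the total time with an abnormality stays at 56 days.

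**Step 3: who is affected.** All of these must hold: a second treatment-emergent AEOI, the same preferred term, greater severity, and a recorded resolution in between. If the severity is equal or lower, or the term differs, nothing is added. SAP 6.6.4 treats a missing severity as severe, so a missing grade on the second record after a mild or moderate first event could also trigger the long clock.

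**Step 4: effect on a group summary.** This depends on assumptions that the documents do not supply. Assume uniform timings: episodes of 14-60 days, restart 7-42 days after resolution, and recurrence 20-200 days after restart. Assume also six AEOI patients in an arm. In simulation the arm's median is about 37 days with no qualifying recurrence, about 41 with one, about 47 with two and about 105 with three. The 75th percentile is about 46 days with none, about 52 with one and about 146 with two. One qualifying recurrence therefore moves the quartiles little. It takes two or three among six to move them a lot.

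**The case against.** The strongest reply is that the rule is plainly meant for one episode that worsens, and that reading it across separate episodes is pedantic. The intent is probably right, but the SAP does not state it, and a programmer following the text would join the episodes.

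Several limiting points stand:

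- Protocol 10.3.1 bars restarting study medication after the more serious liver patterns and withholds it after a second elevation, so few patients can have a qualifying recurrence.
- It also permits restarting when tests have stabilized without resolving. The first event may then still be open, and measuring from its start is defensible.
- The analysis is exploratory, with no alpha and no decision rule attached.
- Event counts, laboratory shift tables, liver threshold counts and by-patient listings would let a careful reader spot an inflated time.
- The distortion lengthens apparent events, so it does not hide a liver signal.

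A reader might also infer three stronger things that the documents do not support. First, that the clock always runs from a patient's first AEOI: it does so only in a worsening series under one preferred term. Second, that a recurrence is scored as unresolved: only an ongoing most severe event is censored, and one that resolves counts as an event at a longer time. Third, that an arm's median will be badly distorted: that needs recurrence counts and timings that appear nowhere in the protocol or SAP.

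**Conclusion.** The point holds in a limited form and is **minor**. As written, the formula gives a wrong duration when an AEOI resolves and a more severe one with the same preferred term follows. The protocol makes that sequence possible, and the SAP's adjacent rule would treat an equally severe recurrence on the same dates differently. For a resolved earlier episode the error is always in the direction of a longer time. Its size is the interval from the start of the first episode to the start of the second, 140 days in the worked case.

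The existence and direction of the error rest on the text alone. The day counts rest on assumed dates, and the number of patients affected cannot be derived from the documents. No efficacy analysis or error rate is touched.

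**What to change.** Add one sentence to SAP 10.1.1: the start of the initial event is used only when no resolution is recorded between the successive records; otherwise the time is the resolution date of the most severe event, minus the start of the episode containing that event, plus 1.

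The condition should rest on recorded resolution and not on records abutting to the day. A strict date match would miss overlapping records, which can arise when a missing end day is imputed to month-end under SAP 6.6.3. It would also split one episode when a gap of a few days between records reflects only the testing schedule. Overlapping or continuing records of one worsening episode, including an event that stabilized without resolving, should keep the initial start. A record closed only because its severity changed should not count as resolved.

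Optionally, report by treatment group the number of patients whose abnormality recurred after study medication was re-introduced.

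The cost is one sentence and a small derivation change. The onset and resolution dates are already needed for the planned formula, so no new data are required.

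### The liver AEOI time-to-event analyses count events throughout the study but censor at the end of randomized treatment, so both Kaplan-Meier curves are biased

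*SAP*

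**What the plan says.** SAP 10.1.1 plans two Kaplan-Meier analyses of liver AEOIs, by arm and with confidence intervals for the quartiles: time to first onset, and time to resolution of the most severe event.

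- **Resolution, event:** "the time to resolution will be calculated by the date of resolution of the event", minus the start date, plus one. Nothing cuts resolution dates at the end of treatment.
- **Resolution, censoring:** "Patients whose most severe treatment-emergent AEOI is ongoing will be censored at the date of completion or discontinuation in randomized treatment period". If the cut-off of the data falls sooner, that date is used.
- **Onset, censoring:** "Patients who never reported an AEOI will be censored at the date of completion or discontinuation in randomized treatment period", with the same data cut-off cap. Nothing cuts onsets at the end of treatment.
- **Data window:** SAP 10 states "Unless otherwise noted, all safety analyses will be conducted using on-study data". The TEAE definition in SAP 10.1 has a start but no end. The 30-day window of SAP 10.1.3 covers selected on-treatment summaries, and 10.1.1 does not invoke it.

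Protocol 10.3.1 tells the site what to do when a liver AEOI is found: "Temporarily discontinue study medication". Dosing may restart once the abnormality has resolved or stabilized. For four severe patterns the rule is different: "Patients are not allowed to resume study medication if they have the following". A second elevation after re-introduction also ends dosing. Protocol 6.3.2 encourages visits to Week 114 after a permanent stop, and Protocol 10.7.1 keeps recording adverse events until the patient completes the study.

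**The concern.** Kaplan-Meier needs censoring that is unrelated to the outcome. Take two patients who stop permanently on the same day with an open liver AEOI. One resolves on day 60 and contributes 60 days and an event. The other never resolves and leaves the risk set at the stop, although the site goes on following the event. The second patient is censored at the stop because the event did not resolve.

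This endpoint is exposed to the problem because the AEOI itself interrupts dosing, and its severe forms bar resumption. If the discontinuation date means the last dose, an unresolved severe case may be censored close to onset.

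The onset analysis has the same mismatch. A patient who stops and later has an AEOI is an event. A patient who stops and never has one leaves the risk set at the stop.

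The SAP gives these analyses the purpose of exploring how liver abnormalities relate to study medication. Their curves would understate persistence and overstate onset, more so in an arm with more permanent stops if the arms differ in that respect.

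**Working it through.** The documents state no figure for these analyses, so there is nothing to reproduce. All rates below are assumptions.

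**1. The SAP date formula (date − start + 1) on single cases**

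| Ongoing AEOI | Censored time |
|---|---|
| Permanent stop on the day of onset | 1 day |
| Permanent stop 3 days after onset | 4 days |
| Onset day 100, interruption, resumption, completion at the Week 110 target day 771 | 771 − 100 + 1 = 672 days |
| Onset on day 110, treatment stopped on day 100 | 100 − 110 + 1 = −9 days |

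The third row shows that a patient who resumes is not censored early. The SAP has no rule for the fourth.

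**2. Resolution, 20 AEOIs in one arm**

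Assume 16 resolve on days spread evenly over 14 to 120, and 4 never resolve. Unresolved patients who stop permanently are censored on day 3 under the SAP rule. The others are followed to day 400.

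| Of the 4 unresolved, permanently stopped | Median, SAP rule | Median, follow-up censoring | Resolved by day 180, SAP rule | Resolved by day 180, follow-up censoring |
|---|---|---|---|---|
| 0 | 78 | 78 | 80% | 80% |
| 2 | 71 | 78 | 89% | 80% |
| 4 | 63 | 78 | 100% | 80% |

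**3. Resolution, general form**

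Let u be the share that never resolves and s the share of those permanently stopped on day 3. Resolution among the rest is exponential with mean 40 days, so e^(−3/40) = 0.9277 and e^(−180/40) = 0.0111.

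Censoring at follow-up: S(180) = u + (1 − u) × 0.0111.

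As written: S(180) = S(3) × [(1 − s)u + (1 − u) × 0.0111] / [(1 − s)u + (1 − u) × 0.9277], where S(3) = u + (1 − u) × 0.9277.

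With s = 0.7:

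- u = 0.2. As written: 0.9422 × 0.0689 / 0.8022 = 0.081. Follow-up: 0.2 + 0.0089 = 0.209.
- u = 0.4. As written: 0.9566 × 0.1267 / 0.6766 = 0.179. Follow-up: 0.4 + 0.0067 = 0.407. The medians are 38 and 72 days.

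Unresolved at day 180 is therefore 8% to 18% as written, against 21% to 41%.

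**4. Onset**

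Assume a constant AEOI hazard that continues after the stop, and a share p who discontinue uniformly over the treatment period T but stay on study. Events arise from everyone, while the risk set shrinks to about 1 − p·t/T. For rare events the cumulative hazard is then inflated by −ln(1 − p)/p:

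- p = 0.15: 0.1625 / 0.15 = 1.08
- p = 0.25: 0.2877 / 0.25 = 1.15
- p = 0.35: 0.4308 / 0.35 = 1.23

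Simulation with 3% incidence over 110 weeks gives 8%, 15% and 22%. The formula is slightly high because patients with a later event in fact stay in the risk set until it occurs.

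**The case against.** The strongest reply is that Protocol 10.3.1 requires only a temporary stop at onset. A reader might infer that every unresolved AEOI is censored near day 0 because dosing must stop then. The documents do not support that. Protocol 6.3.1 and 6.3.2 treat interruption and permanent discontinuation separately, SAP 10.2 gives interruption its own date, and a stabilized but unresolved patient may resume. If all unresolved patients resume, the resolution bias disappears (first row of the 20-case table). For elevations above 5 times ULN lasting more than two weeks, and for second elevations, the permanent decision can also come well after onset.

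The date itself is undefined. It could be the last dose, the end-of-treatment visit, the date of the decision, or even discontinuation of the study. The near-onset result needs the last-dose reading.

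A reader might also infer that the worst cases are dropped. They are not: SAP 10.1.1 reports the number censored, the range in days for all patients and the numbers at risk.

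Events will probably be few. At an assumed 3% in about 190 patients per arm (380 / 2), there would be about 6 AEOIs per arm, and the onset inflation would turn 3% into roughly 3.2% to 3.7%. No test depends on these curves. AEOI incidence, the hepatic TEAE summaries, the liver threshold tables and the shifts to worst and last value (SAP 10.1, 10.1.2, 10.4) do not use this censoring rule.

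All of this limits the size of the problem and stands. It does not remove the mismatch between event and censoring windows, the negative times or the undefined date.

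**Conclusion.** The point holds for both analyses. On the natural reading, in which discontinuation refers to treatment, the SAP counts events over the whole on-study period and censors at the end of randomized treatment. Resolution then looks faster and more complete, and cumulative onset is inflated.

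The resolution bias comes from unresolved cases that stop permanently. It is concentrated near onset only if the discontinuation date means the last dose. Patients who resume are not affected in this way.

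The ranges of 8% to 18% against 21% to 41% unresolved, and 8% to 22% relative inflation of onset, rest on assumed rates of non-resolution, stopping and incidence. They show direction and plausible size and are not predictions. The onset range also assumes that the hazard is unchanged off treatment and that those who discontinue remain on study. Nothing in the documents shows that the arms will differ in permanent stops, so a between-arm distortion is possible but not established.

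Since the analyses are exploratory and the number censored is shown, the importance is minor to moderate. It should still be corrected, because the stated rule gives a wrong answer and the data for the right one are already collected.

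**What to change.** In SAP 10.1.1:

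- Censor ongoing AEOIs, and patients with no AEOI, at the last date of adverse event follow-up in the double-blind period (before any first open-label dose) or the data cut-off, whichever is earlier. This also removes the negative times, because follow-up cannot end before an AEOI recorded during it.
- If an on-treatment version is wanted as well, apply the 30-day window of SAP 10.1.3 to both events and censoring, and define the discontinuation date it uses.

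The cost is one sentence for each of the two analyses and a small programming change. No new data are needed, and no dosing or monitoring rule changes.
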